2. IS THIS RESEARCH SPONSORED OR SEEKING SPONSORED FUNDS?

No, go to question 3

Yes, answer questions within table

IF YES

Provide the name of the sponsor [if NIH, specify department]: **National Institutes of Health, National Cancer Institute**

Is this project receiving or seeking federal funds?

No

Yes

If yes,

Does the grant application, OSP proposal, or "statement of work" related to this project include activities involving human subjects that are not covered within this IRB application?

No, all human subject activities are covered in this IRB application

Yes, however these activities will be covered in future VT IRB applications, these activities include:

Yes, however these activities have been covered in past VT IRB applications, the IRB number(s) are as follows: **20-008, 23-825, 21-1046, 17-896**

Yes, however these activities have been or will be reviewed by another institution's IRB, the name of this institution is as follows:

Other, explain:

Is Virginia Tech the primary awardee or the coordinating center of this grant?

No, provide the name of the primary institution: **Medical University of South Carolina - MUSC**

Yes

3. DESCRIBE THE BACKGROUND, PURPOSE, AND ANTICIPATED FINDINGS OF THIS STUDY:

In 2009, the Food and Drug Administration banned all flavored conventional cigarettes except for menthol cigarettes. Although no such ban exists in the U.S. for E-cigarettes, such efforts have been proposed in several regions[1-3]. Flavors are possible objects of new tobacco control policy. Knowing whether flavors enhance or diminish substitution would be important in evaluating whether to support such bans on E-cigarette flavors. A report from the first wave of the PATH study of tobacco use found that 80% of youth, 73% of young adult and 29% of older adult smokers used flavored products[4]. They also report in that study that over 80% of young adults first used flavored tobacco products while the percentage was approximately 50% among adults. Lastly, the prevalence of current tobacco use among adult ever-users was 32% higher if the first tobacco product they used was flavored [4]. Importantly, one study asked flavored product users what they would do if the product they used was no longer flavored, and reported that 75% would no longer use the product [5]. Clearly, these data show the relevance of user type in understanding potential policies, but also raise the question of whether removal of flavors would result in greater quitting and intention to quit or lead to substitution with some other product.

Purpose: To examine the effects of e-cigarette and cigarette flavors availability on substitutability in the Experimental Tobacco Marketplace.

This study is designed to better understand the effect of possible restrictions in flavored tobacco products. We hypothesize that flavors availability and cigarette/e-cigarette price will affect substitution with other tobacco products differently across groups.

4. EXPLAIN WHAT THE RESEARCH TEAM PLANS TO DO WITH THE STUDY RESULTS:

For example - publish or use for dissertation

The research team plans to publish these results and findings in journals and present at conferences.

5. WILL PERSONALLY IDENTIFYING STUDY RESULTS OR DATA BE RELEASED TO ANYONE OUTSIDE OF THE RESEARCH TEAM?

For example - to the funding agency or outside data analyst, or participants identified in publications with individual consent

No

Yes, to whom will identifying data be released?

6. WILL THE RESEARCH TEAM COLLECT AND/OR BE PROVIDED PARTICIPANT IDENTIFYING INFORMATION (E.G., NAME, CONTACT INFORMATION, VIDEO/AUDIO RECORDINGS)?

No, go to question 7

Yes, answer questions within table

IF YES

Describe if/how the study will utilize study codes: All participant data, including electronic data, will be stored in secure places to protect confidential participant information. Secured places will include locked filing cabinets, locked rooms accessible only to study personnel, and/or password-protected databases. Moreover, all data will be quality controlled in preparation for data analyses. All discrepancies in data entry will be checked against the raw data source, and the correct data entry will be used. All data entered into spreadsheets and databases will be coded by participant ID number and not by name (i.e., first and last name).

If applicable, where will the key [i.e., linked code and identifying information document (for instance, John Doe = study ID 001)] be stored and who will have access? All entered data will be backed up on secure password-protected servers. Computers used in the studies will also be password protected, accessible only by study personnel. IRB regulations will be strictly adhered to in the conduct of the proposed research. Specifically, prior to implementation of any protocol changes, amendments will be submitted to the IRB for approval.

Note: the key should be stored separately from subjects' completed data documents and accessibility should be limited.

7. HOW WILL DATA BE STORED TO ENSURE SECURITY (E.G., PASSWORD PROTECTED COMPUTERS, ENCRYPTION) AND LIMITED ACCESS?

To secure study data computer databases will have coded identifiers, only ID numbers will be used, data will be kept in secure locations and/or in locked offices. The study team will have access to data that participants' identities could be readily ascertained, such as in screening information and previous participant payment information. Participants names, however will not be used during any data analysis nor will they be part of any published results. Only authorized study personnel will have access to screening and payment information.

The only key connecting participants' data ID to their identities is in REDCap, which is accessible only to trained personnel and is accessed via secure log in.

8. WHO WILL HAVE ACCESS TO STUDY DATA?

Access to study data will be limited to study personnel who have completed the IRB Human Subjects Training and who have been delegated the responsibility of data collection, management, or analyses by the PI.

9. DESCRIBE THE PLANS FOR RETAINING OR DESTROYING STUDY DATA:

Data collected from this study will be retained and destroyed in accordance with state and federal law that requires a 5-year retention period following study closure.

10. FROM WHERE DOES THE EXISTING DATA ORIGINATE?

The existing data comes from Qualtrics survey responses and our Experimental Tobacco Marketplace dataset collected under VT IRB 20-008.

11. PROVIDE A DETAILED DESCRIPTION OF THE EXISTING DATA:

Data for this project is comprised Qualtrics survey data and data from our Experimental Tobacco Marketplace. All data were collected under VT IRB 20-008, including obtaining informed consent.

12. IS THE SOURCE OF THE DATA PUBLIC?

No, go to question 13

Yes, you are finished with this application

13. WILL ANY INDIVIDUAL ASSOCIATED WITH THIS PROJECT (INTERNAL OR EXTERNAL) HAVE ACCESS TO OR BE PROVIDED WITH EXISTING DATA CONTAINING INFORMATION WHICH WOULD ENABLE THE IDENTIFICATION OF SUBJECTS:

- Directly (e.g., by name, phone number, address, email address, social security number, student ID number), or
- Indirectly through study codes even if the researcher or research team does not have access to the master list linking study codes to identifiable information such as name, student ID number, etc
or
- Indirectly through the use of information that could reasonably be used in combination to identify an individual (e.g., demographics)

No, collected/analyzed data will be completely de-identified

Yes,

If yes,

Research will not qualify for exempt review; therefore, if feasible, written consent must be obtained from individuals whose data will be collected / analyzed, unless this requirement is waived by the IRB.

Will written/signed or verbal consent be obtained from participants prior to the analysis of collected data? Yes, signed consent has been obtained

This research protocol represents a contract between all research personnel associated with the project, the University, and federal government; therefore, must be followed accordingly and kept current.

Proposed modifications must be approved by the IRB prior to implementation except where necessary to eliminate apparent immediate hazards to the human subjects.

Do not begin human subjects activities until you receive an IRB approval letter via email.

It is the Principal Investigator's responsibility to ensure all members of the research team who collect or handle human subjects data have completed human subjects protection training prior to handling or collecting the data.

-----END-----

Official Title of Study:

Effects of Cigarette and E-cigarette flavors on Substitutability in the Experimental Tobacco Marketplace (20-008)

ClinicalTrials.gov Identifier (NCT Number):

NCT06910202

Document Type:

Statistical Analysis Plan

Document Date:

09/09/2025

Principal Investigator (PI):

[name]

Sponsor/Collaborator:

Medical University of South Carolina

Confidentiality Statement:

This document does not contain names of research participants.

Statistical Analysis Plan

Demographic characteristics (e.g., age, race, income) and smoking-related assessments (e.g., FTCD, QSU, PHR) were described using mean, standard deviation, and percentages. For each of the product categories in the ETM, we sought to determine if the policy restrictions differentially impacted cigarette, e-cigarette, oral tobacco and nicotine products, and NRT product purchasing. We used a hierarchical linear regression to evaluate differences in purchase behavior, which considered a three-way interaction among the cigarette policy condition, the e-cigarette policy condition, and the price of the manipulated commodity (log-transformed), and a random effect for the participant. We performed model selection to determine which set of variables (i.e., cigarette policy condition, the e-cigarette policy condition, and the price of manipulated commodity), which interactions among these variables, and the degree of these interactions were supported by the data. Specifically, we performed an exhaustive search of the model space and selected the optimal model as that with the lowest Bayesian Information Criterion (BIC). Model posterior probabilities (PP) were calculated using the BIC as described in Barbieri and Berger [29]. We opted to use the BIC to evaluate model performance because the BIC is model selection consistent. Model summary statistics are reported using Type III sum of squares and Kenward-Roger degrees of freedom [30]. R software Version 4.3.0 was used for all data analysis [31]. All statistical tests were considered significant at the < 0.05 level.

Sample size calculation

The required sample size was calculated a priori. Considering a within-subject Analysis of Variance (ANOVA), where each subject completes all 4 policy conditions, a medium effect size ($f=0.25$) according to Cohen's 1988 conventions, an alpha of 0.05, and 80% power, a total of 24 individuals are required. This calculation was done using G*Power and considered a correlation among repeated measures of 0.5.

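### Does the SAP's question about differential impact on four product categories need a model that compares the categories?

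*SAP*

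**What the plan says.** The SAP's analysis section states its aim in one sentence, which begins "For each of the product categories in the ETM, we sought to determine if the policy restrictions differentially impacted cigarette, e-cigarette". The question it poses, with all four categories, is whether "policy restrictions differentially impacted cigarette, e-cigarette, oral tobacco and nicotine products, and NRT product purchasing". The full model contains a "three-way interaction among the cigarette policy condition, the e-cigarette policy condition, and the price of the manipulated commodity (log-transformed") and a random effect for participant. The exhaustive BIC search then decides "which set of variables (i.e., cigarette policy condition, the e-cigarette policy condition, and the price of manipulated commodity") are retained, with which interactions. That list is closed, and product category is not on it. The section ends: "All statistical tests were considered significant at the < 0.05 level".

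In the protocol, question 3 gives the purpose as "To examine the effects of e-cigarette and cigarette flavors availability on substitutability in the Experimental Tobacco Marketplace". Its background asks whether removing flavors would lead people to quit or "lead to substitution with some other product". The hypothesis in the same answer concerns differences across groups, a term left undefined there. It does not mention differences across product categories.

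The sample size section considers a within-subject ANOVA over four policy conditions and states "an alpha of 0.05, and 80% power, a total of 24 individuals are required". It has no product-category factor.

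**The concern.** The grammatical object of the SAP's verb is the list of four categories, so the aim can be read as asking whether a policy moves one category more than another. Substitution also involves two products, which encourages that reading. On it, the plan has no matching analysis: no policy-by-category term, no joint model and no contrast across categories.

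What would be left is to set four sets of results side by side and note where a policy term survived. A term that is significant in one category and absent in another does not show that the two effects differ. If all four true effects were equal, the verdicts could still disagree often, and a reader could take that for a differential effect.

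**Working it through.** **1. The SAP's own figure.** Inputs from the sample size section: f = 0.25, four conditions, correlation 0.5, alpha 0.05. Sphericity is assumed, as the SAP does not mention it. The noncentrality is λ = f² × N × m / (1 − ρ) = 0.0625 × 24 × 4 / 0.5 = 12, with 3 and (24 − 1) × 3 = 69 df. Power is 0.817 at N = 24 and 0.797 at N = 23. The stated 24 is reproduced.

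**2. How often verdicts disagree when nothing differs.** Suppose the same true effect in all four categories and power p for each category's policy test. With independent categories, the chance that the four verdicts are not all alike is 1 − p⁴ − (1 − p)⁴.

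- p = 0.80: 1 − 0.4096 − 0.0016 = 0.589. For two categories: 2 × 0.8 × 0.2 = 0.32.
- p = 0.817: 0.55.
- p = 0.50: 0.875.
- p = 0.95: 0.185.

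With p = 0.80 and correlation −0.2 / 0.5 / 0.8 between category estimates, simulation gives 65% / 41% / 26%.

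**3. Whether 80% is the right p.** The SAP's 80% belongs to a 3-df test across four conditions. A single policy factor, if the four conditions are read as 2×2, is a 1-df test. Keep λ = 12 and use 23 or 69 error df:

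| Where the effect lies | λ for one policy | Power (23 to 69 df) | Disagreement among four, independent |
|---|---|---|---|
| All in one policy | 12 | 0.91 to 0.93 | 31% to 26% |
| Split equally between two policies | 6 | 0.65 to 0.68 | 81% to 78% |

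The same sample-size inputs therefore allow anything from about 26% to 81% before correlation is considered. Independence is also doubtful, since the same participants buy all the categories.

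**4. The wording, side by side.** The SAP's sentence opens with a distributive phrase: the question is put for each category. That phrase is also the only basis for saying that a separate model is fitted per category, because the SAP never states it outright. It cannot reasonably fix the model structure and be ignored when the aim is read. Taken consistently, the aim is to learn, in each category, whether purchasing depends on cigarette policy, e-cigarette policy, price and their interactions. Those are exactly the candidate terms of the search.

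**5. The substitution question.** Substitution towards another product appears as a rise in that product's purchasing when a flavor is restricted or the manipulated product's price increases. Both are terms in that product's own model. Testing whether the mean change is equal in all four categories is a different question, and equality is an odd null for a study that looks for one category falling as another rises.

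**The case for a change.** The strongest reply is that the cross-category reading remains natural, that the variable list is closed, and that a remedy would be cheap: reword a sentence, or add a participant-level test comparing restricted-minus-unrestricted purchasing across categories (Hotelling's T², 3 and 21 df at N = 24). In simulations with equal effects, that test rejects in 4.7% to 5.1% of trials.

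Part of this stands. No described analysis compares categories, and a claim that a policy affected one category but not another would have no test behind it. A careful reader should not infer a difference from a kept and a dropped term.

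It does not carry the case for a change. The added test needs a purchase unit common to cigarettes, e-cigarettes, oral products and NRT, and the documents give none. It averages over price and so sets aside the interaction at the centre of the SAP's model. It would be post hoc, since the SAP is written in the past tense. It is also weak for some patterns: if one category has an 80%-power effect and another none, power for their difference is 51% with independent categories, and about 47% for the four-category test. Statisticians could reasonably differ on whether it is worth adding. The rewording would leave every planned model and result as it is.

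**Conclusion.** The observation is correct but does not amount to a defect. Product category is not a model variable, and the plan offers no test between categories. The sentence that states the aim nevertheless supports a category-by-category reading, the models answer that reading, and the protocol's substitution question can be answered from the same models. Neither document states a conclusion, or a rule for reaching one, of the form that would mislead.

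The size of the possible misreading is not fixed by the documents. With equal true effects and independent categories it runs from about 26% to 81% under the SAP's sample-size inputs, depending on how the effect divides between the two policies. At 80% power per test it is 58.9%, falling to 41% at correlation 0.5. All of these figures rest on assumed per-category power and correlation.

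What remains is loose wording that analysts would resolve sensibly by fitting and interpreting each category on its own. A direct comparison between categories is an optional extra, subject to a common unit. No change to the plan follows.

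### If BIC keeps a policy-by-log-price term and log price was not centred, the Type III policy test is a contrast at price 1 in an unstated unit, not an average policy effect

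*SAP*

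**What the plan says.** All of the relevant text is in the main paragraph of the SAP. The stated aim is by product category: "we sought to determine if the policy restrictions differentially impacted cigarette, e-cigarette, oral tobacco and nicotine products, and NRT product purchasing". The model is a linear regression with a participant random effect "which considered a three-way interaction among the cigarette policy condition, the e-cigarette policy condition, and the price of the manipulated commodity (log-transformed"). Terms are then chosen from the data: "we performed an exhaustive search of the model space and selected the optimal model as that with the lowest Bayesian Information Criterion (BIC"). For the chosen model, "Model summary statistics are reported using Type III sum of squares and Kenward-Roger degrees of freedom", and "All statistical tests were considered significant at the < 0.05 level".

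The SAP does not give the unit of price, the price points, the form of the log (plain, or with a constant added), any centring or reference price, or the contrast coding of the policy factors. It does not say at which price a policy effect is read when price interacts with policy. The protocol does not describe the price variable. No redaction is visible at this point in the text.

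**The concern.** A Type III test of a factor that also interacts with a continuous covariate tests that factor where the covariate equals zero. Here the covariate is log price, so zero means a price of 1 in whatever unit was logged: a dollar or a cent, per pack or per piece. That price may lie inside the studied range, at its edge or far outside it.

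Two analysts could follow the SAP to the letter on the same data, one in dollars and one in cents, and report different p-values for the same policy, even with opposite signs. The same applies to the policy-by-policy test if the three-way term is kept. Policy effects on purchasing are what the SAP sets out to evaluate, so a reader is likely to take a reported policy test as a statement about the policy over the prices studied.

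**Working it through.** **Inputs from the documents.** 24 participants, 4 within-subject policy conditions, alpha 0.05 (SAP, including its sample size section). **Assumed, because the documents give no prices or effects:** two policy factors with two levels each; five log-spaced prices at 1/4, 1/2, 1, 2 and 4 times a base; plain natural log. This gives 24 × 4 × 5 = 480 rows per model.

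**The plan's own figure.** λ = f²·N·m/(1-ρ) = 0.0625 × 24 × 4 / 0.5 = 12, with df 3 and 69. Power is 81.7% at N = 24 and 79.7% at N = 23, so the stated 24 reproduces. The point below does not depend on it.

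**Algebra.** Write y = … + b1·policy + b2·x + b3·policy·x, with x = log(price). The Type III policy test is H0: b1 = 0, the contrast at x = 0.

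- Multiplying price by k replaces b1 with b1 - b3·ln(k). Dollars to cents is a shift of -4.61·b3.
- In a balanced design SE(b1) is √(1+r²) times its value with centred x, where r = mean/SD of log price.
- Let zm be the policy z at mean log price and zs the policy-by-price z. The z at price 1 is z0 = (zm - r·zs)/√(1+r²).
- Natural log or log10 makes no difference to the p-value.

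**Illustration 1: policy effect with the same sign at every studied price.** The SD of log price is 0.980. Take zm = 5 and zs = 2.5. The effect would cross zero 5/2.5 = 2 SD from the mean, outside the range of ±1.386/0.980 = ±1.41 SD. Since zs² = 6.25 exceeds ln(480) = 6.17, BIC counting rows just keeps the term.

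| Base price, unit | r | SE ratio | z0 |
|---|---|---|---|
| centred | 0 | 1.00 | 5.00 |
| 0.48 | -0.75 | 1.25 | 5.50 |
| 4 | 1.41 | 1.73 | 0.85 |
| 8 | 2.12 | 2.35 | -0.13 |
| 16 | 2.83 | 3.00 | -0.69 |
| 8, logged in cents | 6.82 | 6.89 | -1.75 |

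For example, at base 4: (5 - 1.414 × 2.5)/1.732 = 0.85. With sampling variation added, and among runs that keep the term, the policy test reaches p < 0.05 in 99.9% when centred and in 1% at base 4.

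**Illustration 2: one simulated dataset, base $0.30 per cigarette.** The centred policy estimate is -0.565 (SE 0.129) and b3 = -0.262.

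| Unit | Estimate | p |
|---|---|---|
| centred, or multiple of base | -0.56 | 0.000015 |
| $ per cigarette | -0.88 | 0.00002 |
| cents per cigarette | +0.33 | 0.48 |
| $ per pack of 20 | -0.09 | 0.72 |

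Check: -0.88 + 0.262 × 4.605 = +0.33. The log-likelihood (-831.10) and the policy-by-price p (0.047) are the same in every row. The policy effect is negative at all five prices, from -0.565 + 0.262 × 1.386 = -0.20 to -0.565 - 0.262 × 1.386 = -0.93, yet the test in cents has a positive estimate. One limit: the interaction F is 3.98, so BIC would keep this term if it counts participants (ln 24 = 3.18) but drop it if it counts rows (6.17). With the three-way term added, the policy-by-policy p ranged from 0.12 to 0.67 across units, while the three-way p stayed at 0.199.

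**Illustration 3: an effect that changes sign within the range.** With zm = 2.8 and zs = 3.5 in a random-intercept model on constructed data (3.5² = 12.25, kept under either count), the policy p is 0.0048 centred (+0.24), 0.21 at base 4 (-0.19), 0.047 at base 8 (-0.40) and 0.0021 at base 8 in cents (-1.84). The interaction p is 0.00042 throughout.

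**How often it would arise.** With no true interaction, simulation keeps the term in 0.1% (zm = 0) or 1.1% (zm = 2.8) of runs if BIC counts 480 rows, and in about 2.4% and 6.8% if it counts 24 participants.

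**The case against.** The strongest reply is that the problem may never have occurred. BIC may have dropped every policy-by-price term. Log price may have been centred, or price coded as a multiple of a base, in which case price 1 is a meaningful reference. If the log was of price plus 1, the reference is price 0. A careful analyst would not read a main effect alone beside a kept interaction, and the SAP does not say that one would. All of this stands, and it limits the point to a conditional one. It does not remove it: the SAP promises Type III summaries at 0.05, names none of these safeguards, and specifies no contrasts at chosen prices.

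Four stronger readings are tempting, and the documents do not support them.

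- A reader might infer that the protocol predicts a flavor-by-price interaction. Its question 3 says "We hypothesize that flavors availability and cigarette/e-cigarette price will affect substitution with other tobacco products differently across groups", which concerns differences across groups. The SAP shows only that the interaction was considered.
- A reader might infer that the BIC ranking and posterior probabilities also depend on the unit. That would hold only if the search allowed a policy-by-price term without its policy main effect. The SAP describes choosing variables, then interactions among them, then their degree, which reads more naturally as a hierarchical search, though no such rule is stated.
- A reader might take the changed p-values as false positives. They are valid tests of a real contrast at a price nobody named. At base 4, price 1 is the lowest assumed price, so the contrast there is correctly estimated. In Illustration 3 the policy effect does change sign within the range.
- A reader might think that centring price settles everything. If the policy-by-policy term is kept and the factors use treatment coding, each policy is still tested at the other policy's reference level.

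**Conclusion.** The point holds in conditional form. When a policy-by-log-price term is kept and price is neither centred nor expressed relative to a base, the Type III policy test is the contrast at log price 0 and not the average over the studied prices. The policy-by-policy test is affected in the same way if the three-way term is kept. The shift of -b3·ln(k) rests only on a plain log; the factor √(1+r²) also needs a balanced design.

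Not affected are the highest-order interaction tests, overall fit, BIC among hierarchical models, and any policy factor with no kept price interaction.

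The size in this study cannot be determined, because the documents give no prices, effects or list of kept terms; the number of exposed tests may be zero. The numerical examples show what the written rule permits and do not estimate what happened. This is a change that should be made, not evidence that any reported result is wrong.

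**What to change.** In the SAP:

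1. State the price unit and the exact log transform.
2. Centre log price at its mean over the price points studied.
3. Use sum-to-zero contrasts for both policy factors.
4. State that the search was restricted to hierarchical models, with no interaction entered without its lower-order terms.
5. Where a policy-by-price term is kept, report the policy contrasts with 95% confidence intervals at named prices, such as the lowest, central and highest, from the same fitted model, instead of relying on the main-effect F.

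If log price was already centred and sum-to-zero coding used, saying so settles the main-effect tests. The cost is a few sentences and re-reporting from the same data. Model selection would need rerunning only if the search was not hierarchical.

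### Each participant completes all four policy conditions, but condition order is in neither the stated model nor the BIC search

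*SAP*

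**What the plan says.** The SAP's sample size section sets out a within-subject ANOVA "where each subject completes all 4 policy conditions". It assumes "a medium effect size ($f=0.25$) according to Cohen's 1988 conventions", "an alpha of 0.05, and 80% power, a total of 24 individuals are required", and it "considered a correlation among repeated measures of 0.5".

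The SAP's analysis section fits a hierarchical linear regression with up to a three-way interaction among cigarette policy, e-cigarette policy "and the price of the manipulated commodity (log-transformed), and a random effect for the participant". An exhaustive BIC search then chooses among models built from a closed list of variables: "i.e., cigarette policy condition, the e-cigarette policy condition, and the price of manipulated commodity". Order, period and sequence are not on that list, so order cannot enter through model selection either.

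Neither document mentions randomised or counterbalanced condition order. Protocol items 10 and 11 say that the data were collected under an earlier approval, VT IRB 20-008, which is not among the documents supplied. The SAP is dated 09/09/2025 and describes the analysis in the past tense.

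**The concern.** Every policy contrast compares a person with himself or herself at different positions in a series of four. If purchasing changes with position, for whatever reason, a model without order has nowhere to put that change except the residual or the policy effects.

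- **Order balanced across participants:** the trend goes into the residual. Tests become conservative and power is lost.
- **Order randomised per participant:** the trend is noise within persons. With one observation per condition the test keeps its size but loses power. With several price observations per condition, the noise is shared by all rows of a condition while the model treats the rows as independent given the participant. The policy test can then reject too often.
- **Order the same for everyone:** trend and policy are the same contrast, and no model term separates them.

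**Working it through.** **Inputs.** From the SAP's sample size section: N=24, m=4 conditions, f=0.25, ρ=0.5, α=0.05. Assumed, because the documents give no figure: a linear drift of d within-person SDs per position, and k price rows per condition.

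**1. The plan's own figure.** The noncentrality is λ = N·m·f²/(1−ρ), with 3 and 3(N−1) degrees of freedom.
- N=24: λ = 24×4×0.0625/0.5 = 12, df 3 and 69, power 81.7%.
- N=23: λ = 11.5, df 3 and 66, power 79.7%.

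So 24 is the smallest N that reaches 80%. The stated sample size reproduces.

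**2. Cost of an order term.** Under balanced order the term is orthogonal to policy. λ stays at 12, error df fall from 69 to 66, and power goes from 81.7% to 81.6%. Under unrestricted random order the balance is only approximate. With no drift, 4,000 simulated trials gave 81.5% without the term and 79.9% with it, a cost of one to two points.

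**3. Cost of leaving order out: randomised order, one row per condition.** The four positions contribute −1.5d, −0.5d, 0.5d and 1.5d. Their sum of squares per person is (2.25+0.25+0.25+2.25)d² = 5d² on 3 within-person df. Error variance is therefore multiplied by 1 + 5d²/3 = 1 + 1.67d², and λ is divided by the same factor.

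| d | Variance factor | λ | Power, no order term |
|---|---|---|---|
| 0 | 1.000 | 12.00 | 81.7% |
| 0.1 | 1.017 | 11.80 | 81.0% |
| 0.2 | 1.067 | 11.25 | 78.9% |
| 0.3 | 1.150 | 10.43 | 75.5% |
| 0.5 | 1.417 | 8.47 | 65.4% |

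Simulation agrees: without the term, 75% at d=0.3 and 66% at d=0.5; with it, 80% at both. Type I error stayed near 5% either way.

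**4. Several price rows per condition: randomised order, participant effect only.** Here d is in units of the row-level residual SD, and there is no true policy effect. Relative to the row-level variance, the expected policy mean square is 1 + 1.67kd². The remaining drift is spread over the error df, so the expected error mean square is 1 + 23×5kd²/ν, with ν = 24(4k−1) − 4 (three df for policy, one for price). With R the ratio of the two, the approximate rejection rate is P(F > F_crit/R) on 3 and ν df.

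| k | d | ν | Policy MS | Error MS | R | Type I error |
|---|---|---|---|---|---|---|
| 2 | 0.1 | 164 | 1.033 | 1.014 | 1.02 | 5% |
| 2 | 0.3 | 164 | 1.300 | 1.126 | 1.15 | 8% |
| 2 | 0.5 | 164 | 1.833 | 1.351 | 1.36 | 12% |
| 5 | 0.1 | 452 | 1.083 | 1.013 | 1.07 | 6% |
| 5 | 0.3 | 452 | 1.750 | 1.114 | 1.57 | 17% |
| 5 | 0.5 | 452 | 3.083 | 1.318 | 2.34 | 34% |

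For d of 0.3 and 0.5, simulations of the same setting gave 8% and 12–13% with two prices, and 17–19% and 33–36% with five. Adding the order term brought every case back to about 5%.

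**5. Same order for all.** The order and policy columns of the design coincide, so the term cannot be estimated and no calculation rescues the contrast.

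**The case against.** The strongest objection is that the case turns on facts held elsewhere. The data come from a study whose protocol is not supplied, and that is where the order of conditions would be described. This stands as a limit on the size of the problem. It does not answer the omission, because the model is specified in this SAP and would be fitted without order however the conditions were assigned.

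Second, the documents mention no sessions, learning or fatigue; the four conditions may have been done in one sitting. The point is therefore framed as condition order, and the drift is an assumption. In the SAP's units, drift d corresponds to a spread of position means of d×√1.25×√0.5 = 0.79d. That is 0.24 at d=0.3 and 0.40 at d=0.5, against a policy effect of 0.25. A material power loss needs a trend about as large as the effect sought; at d=0.1 the loss is under one point. This also stands.

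Third, if the assumed correlation of 0.5 already reflects order variation, the stated power already includes the loss in step 3, and an order term would be a gain on top. The documents do not settle this.

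Fourth, steps 1 to 3 use the four-condition omnibus test, and step 4 a simplified version of the SAP model with no policy-by-price interactions and no BIC selection. The figures indicate direction and rough size only.

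A reader might infer that the policy effects are confounded with order and that false positives are likely. The documents do not support that: nothing in them shows a fixed order. With exact counterbalancing the omission makes tests conservative. Nor does the point imply that 24 participants is a wrong sample size.

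**Conclusion.** The omission is a fact of the text: order is in neither the model nor the search. Its effect is conditional. Under randomised order with one row per condition it costs power only: under one point at d=0.1, about 6 points at d=0.3 and about 16 at d=0.5. With several price rows and only a participant effect, randomised order alone does not protect the type I error, which reaches roughly 8–13% with two prices and 17–34% with five for d of 0.3 to 0.5. These sizes rest on an assumed linear drift, assumed row counts, N=24 and the SAP's f and ρ.

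The change is worth making because the term is cheap and protects against both outcomes. The unknowns are how order was assigned and how large any trend is. If order was fixed, the remedy is a limited conclusion, not a model term.

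**What to change.** 1. State how condition order was assigned and the number of participants on each order.
2. If order varied, add condition order (1 to 4, categorical) as a fixed effect retained in every candidate model, outside the BIC search. Alternatively, keep the reported model and give an order-adjusted sensitivity analysis beside it. Label either one post hoc, since the SAP describes the analysis as already done.
3. If all participants had the same order, state that policy and order cannot be separated, and limit the conclusion accordingly.

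A comparison restricted to each participant's first condition would leave about 24/4 = 6 people per condition. It can be shown descriptively but is not a test of anything.

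The cost is three degrees of freedom, at most a point or two of power if there is no trend, and one variable taken from existing records. It requires that order or time stamps were kept. No new data are needed.
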